## **6 ASSESSMENTS**

Assessments will take place in the Nuclear Medicine Department and in the Rheumatology department CHUV, Lausanne, Switzerland.

Subjects will be evaluated for safety and tolerability in accordance with Table 1 and the following Visits Schedule:

- Voluntary written informed consent will be obtained from every subject prior to the initiation of any study-related procedures.
- Each subject's demography: gender, ethnicity, weight, height, medical history, and relevant baseline characteristics will be recorded at screening visit.
- Inclusion/exclusion criteria will be checked at Screening.
- Women of childbearing potential must have negative urine pregnancy test at screening and before each 99mTc-rhAnnexin V-128 administration.
- All patients will have a baseline DPD-99m-Tc bone scan prior to any treatment. Patients will also perform a 3 hours post injection whole body scan as described below (Imaging section). The 99mTc-DPD bone and whole body scan are not required in case the patients already performed them within 8 weeks prior to the 99mTc-rhAnnexin V-128 administration.
- Vital signs will be taken at all study visits.
- ECGs will be recorded at all study visits except for Day 56 visit to measure the different ECG intervals (RR, PR, QRS, and a more extended QT evaluation according to ICH E14, and heart rate, HR). A single ECG will be taken supine, after 5 minutes rest, and not immediately after a meal. The parameters will be measured as a mean value of minimally 3 beats. The Investigator will note in the CRF whether the ECG is normal or abnormal, as well as the clinical relevance of abnormal ECGs. Clinically relevant abnormalities will be recorded on the Adverse Event page of the CRF.
- Physical examination will be conducted at Screening, Day 42 and Day 90.

- BASDAI, BASFI, BASMI for AS, DAS28 Disease Activity Score assessments for RA will be performed at baseline, Day 42 and Day 90.
- Blood samples for haematology, coagulation, biochemistry and urinalysis will be obtained at screening, at Day 30, Day 42 and Day 90, as described in the table below. For PK subgroup of patient's blood samples will also be collected pre-injection, 24 hours post injection as described above.
- All medications taken from 2 weeks prior to the first administration date through the end of study are to be recorded as medical history and concomitant medications, included therapies for RA and AS
- Any adverse events post-injection will be followed until resolution. 24 hours after each treatment injection (at Day 2 and Day 43), each patient will be contacted by phone (except at Day 2 for patients participating in the PK and dosimetric sub-study who will be interviewed during in site visit) in order to inquire if they experienced signs or symptoms of allergic reactions (edema, rash).

**In more details, all patients will undergo the following assessments:**

**General laboratory analysis** will be performed and blood samples collected at screening, on Day 30, Day 42 and Day 90 Table 2 summarizes general laboratory analysis to be performed.

Haematology	Coagulation	Blood Chemistry	Urinalysis

• WBC with differential

• Platelets

• Hb

• MCV

• Haematocrit

	

• PT

• PTT

• INR

	

• BUN

• Serum creatinine

• Creatinine Clearance

• Uric acid

• Albumin

• Total bilirubin

• AP

• AST/ASAT

• ALT/ALAT

• Gamma-GT

• Sodium

• Potassium

• LDH

• GlycoHb

• fT4

• CRP

• Calcium

• Glucose

	

• RBC/hpf

• WBC/hpf

• Casts/lpf

• Protein by dipstick test

• Pregnancy test (at screening, if applicable and before injection of study product)

**Clinical assessment**

For RA diagnosed patients a clinical evaluation will be made at the screening visit, at Day 42 and Day 90. The DAS-28 (3items: tender joints, swollen joints and ESR) will be calculated. For AS beside the clinical evaluation including the search for enthesopathy – using the Maastricht Score -, assessments with BASDAI, BASFI and BASMI will be made.

The clinical assessment will be completed by the measurement of biological markers of inflammation (ESR, CRP and CBC).

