### **3 STUDY DESIGN**

#### **Study Outline**

This is a monocentric, open label, Phase I-IIa study.

Patients who have signed the informed consent and are eligible for study participation according to the inclusion and exclusion criteria will receive a single intravenous bolus of 99mTc-rhAnnexin V-128 on Day 1 and a single intravenous bolus of 99mTc-rhAnnexin V-128 6 weeks later (+/- 2 weeks).

All patients will start a new RA or AS treatment on Day 2.

In order to minimize the risks for the study population, patients will be enrolled with a minimum of 2-week interval.

Details on study assessments are provided in Protocol Section 6 and Table1.

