### **Details on treatment of the patients:**

Patients with RA will be diagnosed based on ACR/EULAR10 and will thereafter be evaluated with DAS 28. Patients with AS will be diagnosed based on the ASAS criteria. Each patient will be anonymized and identified with a patient ID number.

A unique subject identification number (Patient ID) will be assigned at the start of the Screening Period to each subject who signs the informed consent form until the study termination of the patient. This number will identify the subject throughout the study.

Patient IDs will include the 2-digit country code number (SW) and a 3-digit subject number (ex: SW001 for first subject In).

In both groups of patients – i.e. RA and AS patients – the introduction of a Bi-DMARD treatment should be indicated at the moment of inclusion in the study. The Bi-DMARD therapy should start on Day 2 of the study. RA patients must have been treated at least with one DMARD (methotrexate, leflunomide and sulfasalazine) or a combination of them in the last 3 months – before inclusion - and this/these DMARD(s) will be continued in this study. Otherwise, RA patients must have been previously treated with Bi-DMARD before administration of the new Bi-DMARD treatment. The non-response of the previous Bi-DMARD treatment must be documented.

AS patients must at least have been treated with NSAID in the last 3 months before inclusion and they

should be under the same NSAID treatment during the last 4 weeks before inclusion.

For RA patients, anti-tumour necrosis factor (TNF) antibodies, anti-interleukine 6 (IL-6) antibodies and abatacept therapies are to be considered and are authorized in Switzerland as first line Bi-DMARD agents in RA. On the contrary, anti-CD 20 positive lymphocytes antibodies can only be used, if one anti-TNF therapy failed.

In the AS patients group, only anti-TNF antibodies can be considered, if NSAID are not sufficient.

Ten patients enrolled in the study will be asked to participate in a dosimetry and PK sub-study, irrespective of the group they are part of (RA or AS).

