**Ultrasound assessment**

For RA patients only, an ultrasound examination of the 28 joints included in the DAS 28 will be made at screening, Day 42 and Day 90. Synovitis, power-doppler activity and erosions will be checked.

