7.16 Disease Assessment

BASDAI, BASFI and BASMI scores for AS patients will be presented as a descriptive table at each visit.

DAS28 and ACR/EULAR scores for RA patients will be presented as a descriptive table at each visit.

7.17 ^{99m}Tc -rhAnnexin V-128 Scintigraphy

Descriptive statistics of the imaging findings with report of location and intensity of lesions at each imaging time point will be reported to determine the most suitable imaging time point post injection.

An association between annexin scintigraphy results and disease assessments (see Section 7.16) will be presented to assess diagnostic concordance.

These analyses will be taken care of by AAA's study physician and results will appended to the clinical study report.

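### DAS28 with ESR is the only RA activity index in the SAP's scan-concordance analysis, although anti-IL-6 biologics may start between the two scans and the 28-joint ultrasound is left out

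*Protocol*

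**What the plan says.** **Score.** Protocol section 6, Clinical assessment: "The DAS-28 (3items: tender joints, swollen joints and ESR) will be calculated". On timing, the same section says: "For RA diagnosed patients a clinical evaluation will be made at the screening visit, at Day 42 and Day 90".

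**Treatment between the scans.** Protocol section 4, Details on treatment: "For RA patients, anti-tumour necrosis factor (TNF) antibodies, anti-interleukine 6 (IL-6) antibodies and abatacept therapies are to be considered". Protocol section 3 adds: "All patients will start a new RA or AS treatment on Day 2". Scans for all patients are on Day 1 and Day 42 (Table 1), so the new biologic starts between them.

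**Ultrasound.** Protocol section 6 requires for RA patients that "an ultrasound examination of the 28 joints included in the DAS 28 will be made at screening, Day 42 and Day 90", and states: "Synovitis, power-doppler activity and erosions will be checked". Table 1, and the matching schedule in SAP section 5, put ultrasound in the disease-assessment row.

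**Analysis.** SAP 7.16: "DAS28 and ACR/EULAR scores for RA patients will be presented as a descriptive table at each visit". SAP 7.17 plans an association between the scan results and those 7.16 assessments, as a check of diagnostic concordance. It names no statistic and does not say whether levels or changes are compared. Ultrasound does not appear in SAP 6.4, 7.16, 7.17 or the title of Table 14.3.5. Nothing there separates patients by class of biologic.

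**The concern.** The scan measures uptake in joints. Its RA comparator is a composite that mixes joint counts with a blood test. If a permitted treatment acts on the blood test directly, the composite can move while the joints do not. A mismatch between scan and score at Day 42 could then come from the tracer or from the ESR item, and the planned tables would not show which.

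The ACR/EULAR score listed beside DAS28 does not fill the gap. SAP 4.3 describes it as classification criteria, and the protocol uses it for diagnosis, with DAS28 used to evaluate patients afterwards. DAS28 is therefore the only RA activity index in the concordance analysis.

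At stake is the post-treatment part of a secondary imaging objective. The protocol's hypothesis includes assessing response to treatment, so this comparison carries some weight.

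**Working it through.** The plan gives no DAS28 formula, ESR value or expected DAS28 change, so it has no figure of its own to reproduce here.

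**Inputs from the documents**
- DAS28 with three items, ESR being one (Protocol 6).
- Anti-IL-6 permitted; the share of patients on each class is not given (Protocol 4).
- New treatment from Day 2; scans on Day 1 and Day 42; DAS28 at screening, Day 42 and Day 90 (Protocol 3, Table 1).
- 10 RA patients planned (Protocol 2).

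**Assumptions from outside the documents**
- Anti-IL-6 agents lower ESR independently of joint disease.
- Standard 3-item formula: (0.56·√TJC + 0.28·√SJC + 0.70·ln ESR) × 1.08 + 0.16, where TJC and SJC are the tender and swollen joint counts.
- The ESR changes below are illustrative.

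**Step 1: fall in DAS28 from ESR alone.** With joint counts fixed, their terms cancel:

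fall = 0.70 × 1.08 × ln(ESR before / ESR after) = 0.756 × ln(ratio)

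The last column uses a multiplier of 1.10 (0.70 × 1.10 = 0.77), to show that this constant matters little.

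| ESR fall | Example (mm/h) | ln(ratio) | × 0.756 | × 0.77 |
|---|---|---|---|---|
| 2-fold | 20 to 10 | 0.693 | 0.52 | 0.53 |
| 3-fold | 30 to 10 | 1.099 | 0.83 | 0.85 |
| 4-fold | 40 to 10 | 1.386 | 1.05 | 1.07 |
| 6-fold | 30 to 5 | 1.792 | 1.35 | 1.38 |
| 8-fold | 40 to 5 | 2.079 | 1.57 | 1.60 |

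**Step 2: ESR fall needed for 1 point.** exp(1/0.756) = 3.75-fold, or exp(1/0.77) = 3.66-fold with the other multiplier.

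**Step 3: shift in mean DAS28 change.** If k of 10 RA patients take anti-IL-6 and each has a 4-fold ESR fall, the mean shifts by (k/10) × 1.05: 0.10 for k = 1, 0.31 for k = 3, 0.52 for k = 5 and 1.05 for k = 10.

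**Step 4: effect on a scan-to-score correlation.** This is an illustrative simulation with 10 patients, a true DAS28-change SD of 1.0 (assumed), an artefact of 1.07 in k patients and 20,000 repetitions. Entries are mean correlations.

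| True correlation | k = 0 | k = 1 | k = 3 | k = 5 | k = 10 |
|---|---|---|---|---|---|
| 0.7 | 0.68 | 0.64 | 0.60 | 0.59 | 0.68 |
| 0.5 | 0.48 | 0.45 | 0.43 | 0.41 | 0.48 |

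With all ten affected equally, the correlation does not change, because a constant shift does not alter it. The mean change is then biased by the full artefact.

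**Step 5: which comparisons are exposed.** The screening DAS28 and the Day 1 scan both precede the new biologic. The exposed comparison is at Day 42, either as a level or as a change from screening. At Day 90 DAS28 is measured but no scan is scheduled.

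**The case against.** The strongest reply is that the mechanism is not in the documents. Neither one says that anti-IL-6 agents lower ESR apart from their effect on joints. That stands, so the effect is carried here as an assumption and every size depends on it. What does not depend on it is that the SAP compares joint uptake with a composite containing a laboratory item, and leaves out a joint-level measure that is already collected.

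Four stronger readings are tempting, and the documents do not support them.

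- **RA disease is assessed only by DAS28 with ESR.** It is not. The protocol collects ultrasound of the same joints at all three visits, and CRP as well. The gap is in the SAP's analysis.
- **A few anti-IL-6 patients would determine the result.** The simulation shows modest attenuation on average: 0.68 to 0.60 with three of ten affected.
- **Patients would cross the 2.6 activity threshold.** That value is an entry criterion. Neither document applies it at Day 42 or Day 90, so no planned classification would change.
- **Joint counts should displace DAS28 as the main comparator.** That is a preference; nothing in the documents requires it.

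The plan also gives partial protection. RA treatment is recorded at each visit, tabulated by drug name (Table 14.1.6) and listed by subject (Listing 16.2.4.9), and disease assessments are listed too (16.2.4.10). With about ten RA patients, a reader could trace the class of biologic by hand. The contents of Listing 16.2.4.10 are not shown, so the absence of joint components is established only for the summary table. None of this puts an ESR-free comparator into SAP 7.17.

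**Conclusion.** The point holds in a limited form. DAS28 with ESR is the only RA activity index in the SAP's concordance analysis. A class of drug that may act on ESR can be started between the scans, and the ultrasound of the 28 joints is not used.

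Under the two assumptions (a direct effect on ESR and the standard 3-item formula), the distortion per affected patient is about 0.5 for a halving of ESR, 0.8 for a 3-fold fall and 1.35 for a 6-fold fall. A reader might infer that a fall of more than 1 point is typical; it needs ESR to drop by about 3.7-fold or more, and the documents give no ESR data. The number of affected patients is unknown, from none to all RA patients, so the total effect may be zero. The Day 1 comparison is not affected by the newly started drug.

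This concerns a secondary analysis in a study whose primary objective is safety and whose hypothesis tests are all declared exploratory (SAP 7.1.1). It is an inexpensive improvement and does not threaten the study's main conclusion.

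**What to change.** 1. **SAP 7.16 and Table 14.3.5:** for RA patients, add tender joint count, swollen joint count, and ultrasound synovitis and power-Doppler findings, by visit and with change from baseline.
2. **SAP 7.17:** report the scan association with these ESR-free joint measures alongside DAS28.
3. **SAP 7.17:** repeat the post-treatment DAS28 association without patients on anti-IL-6 agents, as a sensitivity analysis, and state how many patients that removes.

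Replacing ESR with CRP is not proposed. It would need its own justification, because the documents do not address whether anti-IL-6 agents affect CRP.

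**Cost.** SAP wording and some table rows. No new data are needed: joint counts are required to calculate DAS28, ultrasound is scheduled, and RA treatment is recorded at every visit. Patient treatment is untouched. The downside is a few more exploratory comparisons in about 10 or fewer RA patients, and the sensitivity analysis may leave very few. The results should be shown descriptively, patient by patient where possible.

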**Ultrasound assessment**

For RA patients only, an ultrasound examination of the 28 joints included in the DAS 28 will be made at screening, Day 42 and Day 90. Synovitis, power-doppler activity and erosions will be checked.

## **Imaging**

Bone scintigraphy: all patients will have a baseline DPD-99mTc bone scan prior to any treatment.. Standard quality control of the camera will be performed every day before patient imaging. Patient will be injected with 9MBq/Kg of DPD-99mTc. Peak will be centered on 140KeV with a 20% windowing; a LEHR collimator will be used. It will be a triple phase bone scan including angiogram, blood pool imaging (10 minutes after injection) and 3 hours delayed imaging. Angiogram will be centered on the most symptomatic joint and/or and associated inflamed tendinous structures; acquisition will be started immediately after DPD-99mTc intravenous injection. Then 16 frames of 15 seconds will be acquired (128x128 matrix; zoom 1). Blood pool images will be acquired 10 minutes after injection and will be centered on the most symptomatic joint. A complement of imaging could be performed at this time centered on another joint. It will be images of 2 minutes (256x256 matrix, zoom 1). Delayed images will be performed 3h post injection. They will be focused on the same joints visualized on blood pool images, with the same acquisition parameters. Centered images will be completed by a whole body scan (10cm/min, 1024x256 matrix; zoom 1). SPECT images could be acquired 3h after injection centred on the most symptomatic joints (60 projections of 10 seconds, 128x128 matrix, zoom 1). On planar images, region of interest will be drawn on symptomatic joints and non symptomatic joints and ratios of activity will be measured. All patients will be subjected to early and delayed planar anterior and posterior images centered on the hands and the feet. On SPECT images, VOI will be drawn on symptomatic joints.

99mTc-rhAnnexin V-128 administrations:patients will be injected intravenously with 250 MBq of 99mTc-rhAnnexin V-128 and then the whole body planar imagings (GE Infinia Hawkeye IV camera, (8 cm/min, 1024x256 matrix; zoom 1) will be performed and repeated acquisitions on symptomatic joints. Standard quality control of the camera will be performed every day before patient imaging. Peak will be centered on 140KeV with a 20% windowing; a LEHR collimator will be used. A dual-SPECT would be acquired centered on the thorax and abdomen at 1h after injection centered (2\*60 projections of 10 seconds each, 128x128 matrix, zoom 1). The use of the whole-body and SPECT data for dosimetry will be discussed further in the Dosimetry section

Semi-quantitative assessment of inflammatory joints will be performed in terms of TBR as well as by calculating the relative uptake between pre and post treatment in ROI/VOIs. ROI and VOI defined and use in the different scintigraphies will strictly have the same pixel size and localization; they will be measured in counts.

In case a suspected anomaly is found at imaging, it would be reported to the rheumatologist and the patient's general practitioner.

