## **Data Review**

All data relating to the study must be recorded in the CRFs provided by the Sponsor. These CRFs should always reflect the latest observations on the patient's participation in the study. Therefore, CRFs are to be completed as soon as possible after (or during) the patient's visit. To avoid inter-observer variability, every effort should be made to ensure that the study determinations are completed by the same individual who made the initial ones at baseline. The Investigator must verify that all data entries in the CRFs are accurate and correct.

The monitor will review the CRFs and evaluate them for completeness and consistency. The CRF will be compared with the source documents to ensure that there are no discrepancies between critical data. All entries, corrections and alterations are to be made by the responsible Investigator or his/her designee. The monitor cannot enter data in the CRFs.

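### Nothing keeps annexin uptake findings from the person who scores disease activity at Day 42 and Day 90, so the follow-up association in SAP 7.17 could be biased upward

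*Protocol*

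**What the plan says.** **Reporting rule.** The annexin part of Protocol Section 6 (Imaging) ends with this rule: "In case a suspected anomaly is found at imaging, it would be reported to the rheumatologist", and also to the general practitioner. It follows the paragraph on semi-quantitative assessment of inflamed joints. The term suspected anomaly is not defined.

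**Clinical scores.** Under Clinical assessment: "For RA diagnosed patients a clinical evaluation will be made at the screening visit, at Day 42 and Day 90". For RA, "The DAS-28 (3items: tender joints, swollen joints and ESR) will be calculated". For AS, besides a search for enthesopathy, "assessments with BASDAI, BASFI and BASMI will be made". Under Ultrasound assessment, for RA only, "an ultrasound examination of the 28 joints included in the DAS 28 will be made at screening, Day 42 and Day 90". None of these sections names the assessor. The opening of Section 6 places assessments in the Nuclear Medicine and Rheumatology departments. Section 11 (Data Review) asks that, as far as possible, "study determinations are completed by the same individual who made the initial ones at baseline".

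**Masking and order.** The trial is open label (Section 3). The plan does not mask the clinical scorer to the scan. The synopsis puts the second scan and the disease scores in the same Day 42 visit without ordering them.

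**Analysis.** SAP 7.17 states: "An association between annexin scintigraphy results and disease assessments (see Section 7.16) will be presented to assess diagnostic concordance". It gives no statistic, visit pairing or unit of analysis. The scores listed in SAP 7.16 are BASDAI, BASFI, BASMI, DAS28 and ACR/EULAR.

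**The concern.** A concordance analysis is informative only if the clinical reference is scored without knowledge of the test. Tender and swollen joint counts are judgements. An examiner who knows which joints took up tracer may be readier to call those joints active, and the association would then partly compare the scan with itself. The exposure is also uneven in time: screening scores precede every annexin scan, while later scores may follow one or two reports. A change from screening could therefore carry the same bias.

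This matters because Protocol Section 2 gives predicting response to treatment as an aim, and its study hypothesis includes assessing response. Response cannot be judged from screening scores alone. It needs the Day 42 or Day 90 scores, which are the ones exposed.

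**Working it through.** **1. What the plan lets us reproduce.** It gives no concordance estimate or target. Its only sample-size arithmetic, 20/(1 − 0.10) = 22.2, rounded up to 23, reproduces but plays no part here.

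**2. Which scores could be exposed**, from the visit schedule:

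| Visit | Annexin scan | Disease scores | Scan result that could be known when scoring |
|---|---|---|---|
| Screening | no | yes | none |
| Day 1 (and 24 h in the sub-study) | yes | no | not applicable |
| Day 42 | yes | yes | Day 1; also Day 42 if the scan is read first (order unstated) |
| Day 90 | no | yes | Day 1 and Day 42 |

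The screening/Day 1 pair is therefore not exposed by this route. Day 90 has no scan of its own, but Day 90 scores could serve as the outcome for an earlier scan.

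**3. Which components could move.** In DAS28 these are the two joint counts; ESR is a laboratory value. The three AS indices are not described as joint counts. Ultrasound and the Maastricht score depend on an examiner, but SAP 7.16 lists neither.

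**4. Illustration of size.** All inputs are assumptions, including a yes/no reading per joint, which the plan does not specify. Kappa = (po − pe)/(1 − pe), where po is observed and pe is chance agreement.

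*Set A: 25% of joints positive on each method, 20% of scan-positive, clinically negative joints re-scored positive.*
- True kappa 0.30: pe = 0.25² + 0.75² = 0.625; po = 0.625 + 0.30 × 0.375 = 0.7375; each discordant cell is 0.2625/2 = 0.13125. Moving 0.20 × 0.13125 = 0.02625 gives po = 0.76375, clinical-positive margin 0.27625, pe = 0.25 × 0.27625 + 0.75 × 0.72375 = 0.6119, and kappa = 0.1519/0.3881 = 0.39.
- True kappa 0: each discordant cell is 0.1875. Moving 0.0375 gives po = 0.6625, pe = 0.25 × 0.2875 + 0.75 × 0.7125 = 0.6063, and kappa = 0.0563/0.3938 = 0.14.

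*Set B: 20% to 40% of joints clinically active, a fraction f of scan-positive, clinically negative joints re-scored positive.*

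| Sensitivity / specificity | f = 0 | f = 0.10 | f = 0.25 | f = 0.50 |
|---|---|---|---|---|
| 0.5 / 0.5 (no association) | 0.00 | 0.06–0.08 | 0.15–0.20 | 0.30–0.40 |
| 0.6 / 0.7 | 0.23–0.30 | 0.30–0.34 | 0.40 | 0.50–0.56 |
| 0.8 / 0.8 | 0.49–0.59 | 0.54–0.62 | 0.61–0.65 | 0.72 |

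One cell worked: 20% active, 0.5/0.5, f = 0.25. The cells 0.10/0.40/0.10/0.40 become 0.20/0.30/0.10/0.40; po = 0.60; pe = 0.5 × 0.3 + 0.5 × 0.7 = 0.50; kappa = 0.10/0.50 = 0.20.

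If the scorer never sees uptake results, f = 0 and there is no bias.

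**5. Timing.** SAP 4.2 reports that recruitment was to stop by the end of September 2017, and the SAP is dated 26 January 2018. A first injection on 30 September 2017 puts Day 90 + 14 days at about 11 January 2018. Allowing four more weeks of screening moves that to about 8 February. Most or all patients had probably finished by the SAP date.

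**The case against.** The strongest reply is that the key link is not in the documents. No section says that the rheumatologist who receives a report also scores joints. The Rheumatology setting and the same-individual request make it plausible, no more. The reporting rule is conditional and goes equally to the general practitioner, who has no scoring role, so it may be meant only for unexpected findings. The uptake ratios are described in a separate paragraph with no instruction to report them. All of this stands. A reader might infer that the plan sends scan findings to the joint scorer and that concordance is inflated; the documents support neither as fact.

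The illustration is also open to challenge. SAP 7.16 tabulates patient-level scores, and SAP 7.17 does not plan a joint-level kappa. Larger values, 0.44 and 0.20 in place of 0.39 and 0.14 in Set A, would require scan-negative, clinically positive joints to be re-scored negative as well. A rule that reports only anomalies would not prompt that, so those values are set aside.

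Finally, the stakes are modest. Testing is exploratory (SAP 7.1.1), the sample is not powered, and SAP 4.2 leaves open whether all secondary analyses will be run. That limits the weight of the point but does not answer it: the term is undefined, the scorer is unmasked, and SAP 7.17 does not confine itself to the unexposed pair.

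**Conclusion.** The point holds as an unaddressed risk. If uptake reports reach the person who scores joints, the DAS28 joint counts at Day 42 and Day 90 could move towards the scan, and associations using those visits could be biased upward. Neither the occurrence nor the size of such bias follows from the documents; the kappa figures show only that moderate re-scoring could produce apparent concordance from none.

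The documented mechanism reaches the examiner-judged part of one RA score. They do not show that it reaches the AS indices, and it does not touch the primary safety objective. The screening/Day 1 pair is clear of this route, although it is not fully independent: annexin acquisition includes extra views of symptomatic joints, and the image reader is not masked either. This is a cheap improvement to a secondary, exploratory analysis, not a threat to the trial.

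**What to change.** **Protocol Section 6, for patients still to be scored.**
- Record Day 42 disease scores before the Day 42 scan.
- Continue to report incidental findings and anything needing care at once.
- Name the scorers. Do not release joint, entheseal or spinal annexin uptake to them until that patient's Day 90 scores are recorded. This must cover the source records too, because Section 11 (Source Documents) requires scans and reports to be kept there; amending the reporting sentence alone would not be enough.

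**SAP 7.17, for all patients.**
- Make screening scores against the Day 1 scan the main concordance pair.
- Flag each patient whose uptake was disclosed before later scoring, and show follow-up associations with and without these patients. The flag must reach the sponsor's study physician, who runs these analyses.

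Where patients have already completed the study, only the SAP changes apply.

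**Cost.** A few sentences, no added procedure or staff, and no change in sample size. Joint-uptake reports are released later, but the tracer is investigational, biological therapy is indicated at inclusion and starts on Day 2, and the protocol ties no treatment decision to uptake. In the main pair, the scores may precede the scan by up to the four-week screening window, though both fall before the new treatment starts.
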